This study aims to identify the preferences of older children (teens and pre-teens) for DNC settings when listening in noise, and if personalization of the DNC feature using the app contributes to reduced listening effort. Subjective preference will be evaluated using blinded A/B comparisons and listening effort will be evaluated using both a subjective slider tool (see Picou, et al 2019) and objective methods (accuracy of words correct and verbal response time for monosyllabic words). Additionally, this study will evaluate speech perception at different DNC settings, from off to strong, which will help inform best practices and recommendations for fittings of older children.

2 Objectives

The primary objective for this study is to determine if DNC "on" at a preferred setting reduces the average *self-perceived* listening effort in teens and pre-teens with mild to severe hearing loss, compared to DNC "off".

The secondary objectives are to determine:

-that DNC "on" at a preferred setting is preferred to DNC "off" when listening in loud noise for teens and pre-teens with mild to severe hearing loss.

- that the majority of teens/pre-teens prefer to use Tap Control to access Bluetooth streaming with their smartphones, compared to using HA push button or phone control.
- that speech intelligibility is maintained with DNC “on”

3 Description of the investigational device

The devices used in this investigation are the Audeo Lumity 90 RICs. The myPhonak app will also be used.

For the purposes of this section, the investigational devices will be considered the hearing aid features of Dynamic Noise Cancellation (DNC) and Tap Control, as these are the specific features being studied for this population. These features are found in the Audeo Lumity devices. DNC is a spatial noise canceller which is currently available on the Audeo Lumity 90 and 70 level devices. The DNC setting is done by the HCP within the Target programming software, or by the end-user via the myPhonak app. The options for setting it range from Off, weak (1-9), moderate (10-16) and strong (17-20).

The overall intended purpose of the device is to amplify and transmit sound of the ear and thereby compensate for impaired hearing. Tap Control enables the hearing aid user to control the access to streaming from the hearing aids via taps on the ear instead of using physical controls.

4 Design of the clinical investigation

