This investigation is a single-group, single site, interventional study. During the lab testing when participants indicate their preference for listening in noise, and during speech performance testing, they will be blinded as to how the hearing aids are programmed. Participants will serve as their own control as DNC “off” will be a condition in which they are tested.

5 Risks and benefits of the investigational device and clinical investigation

There are minimal risks associated with both the investigational device and participating in the clinical investigation. Identified risks are no greater than those associated with the participants personal hearing aids.

The benefits of participating in the investigation include the possibility of hearing sounds not previously heard, and being able to adjust hearing aids to improve communication in noisy environments. Additionally, participation in this study will help to inform future developments and improvements in hearing device technology for this population.

The research personnel will review these risks with the subjects and answer any questions they have. Hearing aids are not a significant risk investigational device as defined in the FDA 21 CFR 812.3(m).

6 Endpoints

The primary endpoint is listening effort, which is determined by multiple measures from the same dual-task paradigm:

- 1) **Subjective rating** of the task by answering the question “How easy was it to listen?” using a visual analog scale with verbal anchors at the end points such as “It was very easy” to “It was not at all easy”.

Secondary endpoints will include the following:

- 1) **Speech Reception Thresholds** is the lowest level, in dB, in which the participant can correctly repeat key words in a sentence. The adaptive HINT-C test will be used with the noise level presented at 67 dB and the target speech signal at varying levels. SRTs will be obtained with the study devices programmed with four different SPiN programs, each one with a different DNC level. The participant's SRT with their own personal hearing aids at their user settings will serve as the control or baseline.
- 2) **Verbal response time** is the length of time it takes the participant to respond verbally to the monosyllabic words presented in noise, while also performing a visual task simultaneously.

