- 3) **Preferences for DNC “on” compared to “off”** will be measured using a forced choice scale A/B comparison. Hearing aids will be programmed with three different SPiN programs, each one with a different DNC setting (off, weak, strong). Participants will be blinded to the settings.
- 4) **Preferences for the use of Tap Control** to access BlueTooth streaming from their smartphone will be measured using a subjective questionnaire which will ask participants to rate which method they prefer: Tap Control, HA push button, or phone control.

7 Inclusion and Exclusion Criteria

Inclusion criteria:

- Children, age 10-17
- Mild, moderate, or moderate-severe binaural sensorineural hearing loss
- Native English speakers with ability to communicate verbally
- Able to read and follow directions
- Access to smartphone and willing to download the myPhonak app to personal smartphone
- Experienced hearing aid users (6+ months)

Exclusion criteria:

- Active middle ear infection
- Unable to follow verbal directions
- Unable to communicate verbally
- Unable to tolerate the physical fit of the device

8 Measurements and procedures

All analyses of the results will occur at the conclusion of the study. Speech scores and subjective questionnaire results will be collected on paper-based forms or electronically through use of a lab-owned tablet. Data from these forms will be entered into an electronic spread-sheet prior to data analysis. It will be stored in a secure Vanderbilt network folder and shared with the Sonova once data analysis is complete on a secure Sonova drive in which only the PI has been granted access.

9 Statistical design and analysis

A power analysis on the primary objective was conducted by the PI using G-Power 3.1. Using an expected effect size for this study of 0.7 (see section 6.3) and assuming a two-condition, repeated

measures study with an alpha level of 5% and a power of 80%, 19 subjects would be necessary. Assuming an attrition rate of 20%, the targeted study enrollment for the primary objective would be 23 participants.

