Listening effort will be measured by a self-report, subjective question, "How easy was it to listen?" in each condition (DNC "off" and DNC "on" at preferred setting) which will be asked following a dual-task activity. This consists of a primary task of monosyllabic word recognition and a secondary task of a physical response to a visual probe. For purposes of this study, the accuracy of the word recognition will be calculated as well as the verbal response time. A generalized linear statistical model will be used in which the ratings will be the dependent variable, which will be predicted by response time and DNC condition. If there is a significant effect of the DNC condition and the mean ratings are better for DNC on at a preferred setting, the claim that DNC reduces self-perceived listening effort can be substantiated.

A general linear statistical model will also be used to analyze the secondary endpoint of objective listening effort. The dependent variable will be response time, and the independent variables will be the type of response time (either verbal response time in repeating the word or dual task response time of a button press to a colored shape) and also the DNC setting. Random effects of participant and trial will be evaluated if the data can support the complexity of the random effects. The claim of reduced listening effort can be substantiated if the verbal response time is significantly shorter with DNC on than with DNC off.

One sided binomial tests against 50% will be used to determine if the preference for DNC on is significantly different from the preference for DNC off, for the first lab task of listening to speech in a noisy environment. Preference will be measured via a blinded A/B comparison.

Preferences for the use of Tap Control compared to other methods of accessing Bluetooth streaming will also be analyzed using a binomial test.

Deviations from this statistical plan will be documented in the final study report with justification. Possible reasons for deviation include missing data and/or violated assumptions (e.g., variance, distribution, etc).

10 Investigation Duration

This study is expected to take approximately 6 months, but will depend on the recruitment rate. The expected duration for each participant is approximately 2-4 weeks.

11 Data handling and management

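### The response-time model names no participant-by-DNC slope, so if children differ in their response to DNC, the test behind the objective-effort claim can reject too often

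*Combined protocol and SAP*

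**What the plan says.** Section 9 states that "A general linear statistical model will also be used to analyze the secondary endpoint of objective listening effort". The dependent variable is response time. The predictors are the type of response time (verbal or button press) "and also the DNC setting". On clustering, the plan says only that "Random effects of participant and trial will be evaluated if the data can support the complexity of the random effects". It gives no criterion for keeping those effects, no fallback, no number of words per condition, and no alpha or sidedness for this test. The decision rule follows: "The claim of reduced listening effort can be substantiated if the verbal response time is significantly shorter with DNC on than with DNC off".

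Two design features matter. Section 4 makes the comparison within child: "Participants will serve as their own control as DNC “off” will be a condition in which they are tested". Section 9 defines the on condition, for the rating taken after the same dual task, as the child's preferred setting. Section 3 describes a device range from weak (1-9) to strong (17-20).

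**The concern.** A random effect of trial makes sense only if the data are held trial by trial, so each child would supply many response times in each condition. A participant intercept then removes how fast a child is overall. It does not remove how much the DNC effect differs from one child to the next. That variation sets the correct error for a within-child comparison, and only a by-participant DNC slope, or an analysis of one difference per child, accounts for it.

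Some such variation is plausible here, because children may prefer different strengths and the sample spans ages 10 to 17 and mild to moderate-severe loss (Section 7). Without the slope, adding words keeps narrowing the standard error even though the number of children is fixed. At stake is a claim of reduced effort on an objective measure, granted on significance alone. An intercept-only fit would be within the plan as written, so the Section 9 requirement to document and justify deviations would not catch it.

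**Working it through.** **The plan's own figure.** For the primary objective, a paired t-test with standardised effect 0.7 and two-sided 5% alpha gives 82.3% power at n = 19 and 79.9% at n = 18. The stated 19 is reproduced. It concerns the subjective rating; it is used below only as the number of children.

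**Inputs.** From the documents: 19 children, each tested with DNC off and on, and a claim decided by significance. Assumed, because the documents are silent: W = 25 or 50 words per condition; trial SD = 1; between-child intercept SD = 0.5; SD of the child-specific DNC effect τ = 0, 0.1, 0.2 or 0.3; balanced data; verbal trials only; no mean DNC effect; two-sided 5% test.

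**Formulas.**
- True variance of the mean on-minus-off difference over N children: (τ² + 2/W)/N.
- Variance assumed by the intercept-only model: 2(1 + τ²/4)/(NW). The τ²/4 is the part of the slope variation that the residual absorbs.
- Ratio of assumed to true variance: r = (2/W)(1 + τ²/4)/(2/W + τ²). N cancels, so enrolling more children does not cure the problem.
- Two-sided rejection rate: 2[1 − Φ(1.96√r)].

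Worked cell, W = 25 and τ = 0.2: r = 0.08 × 1.01/(0.08 + 0.04) = 0.673; 1.96 × √0.673 = 1.608; rejection 10.8%.

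| Words per condition | τ | r | Intercept-only, two-sided | In the shorter direction |
|---|---|---|---|---|
| 25 | 0 | 1.000 | 5.0% | 2.5% |
| 25 | 0.1 | 0.891 | 6.4% | 3.2% |
| 25 | 0.2 | 0.673 | 10.8% | 5.4% |
| 25 | 0.3 | 0.481 | 17.4% | 8.7% |
| 50 | 0 | 1.000 | 5.0% | 2.5% |
| 50 | 0.1 | 0.802 | 7.9% | 4.0% |
| 50 | 0.2 | 0.505 | 16.4% | 8.2% |
| 50 | 0.3 | 0.315 | 27.2% | 13.6% |

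Simulation with 8,000 runs per cell agrees within simulation error. A paired t-test on child means rejects about 5% in every cell.

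**Does losing the participant intercept cause the inflation?** With no participant effect, the assumed variance gains the between-child term 0.5² = 0.25. At τ = 0, r = 1.25, 1.96 × √1.25 = 2.191, and rejection is 2.8%, which is conservative. For τ = 0, 0.1, 0.2, 0.3 the simulated rates are about 3, 4, 7, 13% at 25 words and 3, 5, 12, 22% at 50, below the intercept-only rate in every cell. The missing slope is the cause.

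**Power cost of the child-level test.** If τ = 0, the comparison is between a normal test and a t-test on 18 degrees of freedom. At noncentrality 2.8, power is 80.0% against 75.4%. At 2.5 it is 70.5% against 65.7%, close to the largest gap.

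**The case against.** The strongest reply is that the plan intends to deal with clustering and has merely left the details open. It says random effects will be evaluated, and a reference to their complexity could include slopes. The amount of inflation rests wholly on assumed word counts and variances, and at zero slope variation there is none. Section 6 lists only off, weak and strong for the blinded preference comparison, so children may share one of two on settings; the wider range in Section 3 describes the device, not what was fitted. The planned model also pools verbal and button-press times, and its error rate was not computed here. Unequal trial counts were not examined either. All of this stands, and it limits how firmly the size can be stated. It does not supply the missing term: the plan names participant and trial only, and an intercept-only fit would comply with it.

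Some stronger readings are tempting, and the documents do not support them:
- A reader might infer that the optional participant effect is itself the source of false claims. The check shows the reverse: dropping that intercept alone makes the test conservative.
- A reader might infer that the plan treats words as independent evidence. It does not say so; that would follow only from an intercept-only fit or an unstated fallback.
- A reader might infer that error exceeds 5% whenever children differ. With no participant effect and τ = 0.1, it is about 4% at 25 words and 5% at 50.

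**Conclusion.** The concern holds in a limited form. The plan does not name the term that governs the error of its within-child DNC contrast, and it attaches a claim to that contrast. If the DNC effect varies between children, an intercept-only fit is anticonservative, and increasingly so with more words. Over the assumed range the two-sided rate runs from 5% (no variation) to about 17% at 25 words and 27% at 50. The corresponding chance of a false claim of shorter response time runs from 2.5% to about 9% and 14%. These figures illustrate the mechanism; they are not estimates for this trial. Confidence is medium: the omission is plain in the text, but its size cannot be derived from the documents. The endpoint is secondary, so the primary rating analysis and its sample size do not depend on it. The change should be made before the data are analysed.

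**What to change.** Amend the random-effects sentence in Section 9 to read:

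> The claim is tested by the DNC on-minus-off contrast in verbal response time, from a model with a participant intercept and a by-participant DNC slope, plus a trial effect if supported. If that model does not converge or is singular, the analysis is a paired t-test on each child's mean verbal response time, DNC on minus off.

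This keeps the planned trial effect where the data allow it. It also makes clear that the claim rests on the verbal contrast and not on a DNC effect averaged over verbal and button-press times. The same amendment should state alpha, sidedness and the number of words per condition for this test.

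The cost is a short amendment by the Section 12 route and no new data. If children truly do not differ in their DNC effect, the child-level test gives up to about 5 points of power.

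### The secondary objective-effort claim rests on shorter verbal response time alone; neither word accuracy nor button-press time in the same dual task is a condition of it

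*Combined protocol and SAP*

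**What the plan says.** - **Measures named.** The study aim at the end of section 1 lists the objective measures of effort as "accuracy of words correct and verbal response time for monosyllabic words".
- **Task.** Section 9 describes the dual task: "This consists of a primary task of monosyllabic word recognition and a secondary task of a physical response to a visual probe". It adds that "the accuracy of the word recognition will be calculated as well as the verbal response time". Accuracy is not mentioned again in that section.
- **Endpoint.** Section 6 makes verbal response time a secondary endpoint, which "is the length of time it takes the participant to respond verbally to the monosyllabic words presented in noise" while the child also does the visual task. It does not say whether wrongly repeated words are timed.
- **Model.** In section 9 the outcome is response time. The predictors are the type of response time (verbal or button press) and the DNC setting. No interaction between the two is stated.
- **Claim rule.** "The claim of reduced listening effort can be substantiated if the verbal response time is significantly shorter with DNC on than with DNC off". Nothing else is required.
- **Intelligibility.** Section 2 has a separate secondary objective that intelligibility is maintained. Its endpoint in section 6 is the HINT-C speech reception threshold. Section 9 gives that objective no analysis and does not tie it to the effort claim.

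**The concern.** In a dual task, the time to repeat a word can fall for reasons other than lower effort. Children as a group may answer sooner and get more words wrong, or may give the words priority and respond later to the probe. The trial collects both measures that would expose this, and neither can change the conclusion. A result with shorter verbal time and clearly worse accuracy would still be written up as reduced listening effort, against one of the two objective measures the plan names.

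The accuracy route is the firmer one, because accuracy appears in no analysis at all. The button-press route is weaker, because that time is at least in the model.

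**Working it through.** **1. What each dual-task measure does in the plan**

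| Measure | Named as objective effort (section 1) | In a section 9 model | Condition of the claim |
|---|---|---|---|
| Verbal response time | yes | yes | yes, the only one |
| Word accuracy | yes | no | no |
| Button-press time | no | yes | no |

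**2. The plan's own figure.** Section 9 gives 19 children for an effect size of 0.7, alpha 5% and power 80%. A two-sided paired t-test (noncentral t) at 0.7 has power 79.9% with 18 and 82.3% with 19, so 19 is reproduced. The stated 23 is 19 × 1.2 = 22.8, rounded up. These figures concern the self-rating. The documents give no effect size or SD for response time or accuracy, so the steps below borrow only n = 19 and use assumed effects.

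**3. How often a pure trade-off meets the rule.** Let dz be the mean paired difference (off minus on) divided by its SD. With 18 degrees of freedom the two-sided 5% critical value is 2.101, and

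P(significantly shorter) = 1 − F(2.101; 18 df, noncentrality dz × √19).

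| Assumed dz on verbal time | Noncentrality | P(rule met) |
|---|---|---|
| 0 | 0 | 2.5% |
| 0.2 | 0.87 | 13% |
| 0.3 | 1.31 | 24% |
| 0.5 | 2.18 | 54% |
| 0.7 | 3.05 | 82% |

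The probability is the same whether the shift comes from lower effort or from a trade-off. The rule cannot tell them apart.

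**4. Effect of adding conditions, at dz 0.7 on verbal time.** Products assume independent measures. Ranges are from simulation with assumed correlations of up to 0.5 in size between the paired differences.

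| Situation | Rule as written | Plus: neither other measure significantly worse | Plus: neither other mean worse at all |
|---|---|---|---|
| True benefit, other two unchanged | 82% | 0.823 × 0.975² = 78%; range 78–80% | 0.823 × 0.5 × 0.5 = 21%; range 21–32% |
| Trade-off, equal loss on one measure | 82% | 0.823 × 0.177 × 0.975 = 14%; range 11–17% | near 0 |
| Trade-off, equal loss on both | 82% | 0.823 × 0.177² = 2.6%; about 3% | near 0 |

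Here 0.177 = 1 − 0.823 is the chance that an equal loss is not significant, and 0.975 is the chance that an unchanged measure does not look significantly worse.

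**5. Does having button-press time in the model protect the claim?** If only main effects are fitted, the DNC coefficient averages the two response types. With equal SDs, an equal slowing of the button press cancels it, and it is significant in the favourable direction in about 2.5% of simulated trials. But that average is not the verbal contrast the rule names. Estimating that contrast needs an interaction or a separate model, and the protection then goes. Neither version guards against lost accuracy. With accuracy down and button-press time unchanged, the averaged coefficient is still significant in about 53% (correlation 0) to 82% (correlation −0.5 between the two times' improvements) of trials.

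**The case against.** - **One prespecified measure per claim is legitimate.** Section 6 lists verbal response time and does not list word accuracy, the claim is secondary, and the primary claim rests on self-rating. This stands as a reason to treat the point as a recommended change. It does not make verbal time interpretable alone when the plan itself names accuracy beside it.
- **A trade-off is speculative.** This stands. Children are their own controls and, under section 4, blinded during speech performance testing. If that covers the dual task, a deliberate change of strategy is less likely, although blinding does not exclude a shift caused by the sound itself. Wrong answers might also be slower, through hesitation. More errors would then lengthen mean verbal time and work against the claim.
- **Accuracy is calculated, so a fall could be seen.** True, but nothing in the plan lets it alter the conclusion.
- **Intelligibility has its own objective.** The HINT-C is a sentence test run separately, so it cannot detect a trade-off inside the dual task.
- **A gate could block true benefits.** This stands against a gate that requires the observed means not to be worse, which would grant a true benefit only 21–32% of the time. It has little force against a gate of no significant worsening (78–80%).

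A reader might infer that an individual child who answers faster but less accurately is counted as showing reduced effort. The documents do not support this, because the rule is a test on the group. Nor do they support inferring that verbal time will be biased in favour of DNC.

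**Conclusion.** The point holds as a gap in the claim rule for a secondary endpoint. Shorter group verbal response time is sufficient by itself. Accuracy can have no influence, and button-press time is not a condition. A trade-off visible in the trial's own data would still count as reduced listening effort.

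The size is illustrative. At n = 19 and two-sided 5%, a pure trade-off would meet the rule in 24%, 54% or 82% of trials at an assumed dz of 0.3, 0.5 or 0.7, against 2.5% with no shift. The 0.7 is the effect size planned for another endpoint, and the correlations are assumed. The likelihood and direction of a trade-off cannot be judged from the documents. The sample size and the primary claim are not affected by this point.

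**What to change.** In section 9:

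1. Base the verbal on–off contrast on correctly repeated words, with all trials as a sensitivity analysis. State how the contrast is obtained: a type-by-DNC interaction or a separate verbal model.
2. Analyse word accuracy and button-press time by DNC condition in the same runs.
3. Grant the objective claim only if verbal time is significantly shorter and neither accuracy nor button-press time is significantly worse with DNC on, or worse by more than a prespecified margin. Otherwise report a trade-off.

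The significance gate is simple but misses small losses: at n = 19 a loss of dz 0.3 would be flagged only about 24% of the time. A margin is more informative if the sponsor can justify one. A gate on observed means alone should be avoided for the reason shown above.

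The cost is SAP wording and modest analysis, since all three measures are already collected. With the significance gate, the chance of granting a true benefit falls slightly, from about 82% to 78–80% at an assumed dz of 0.7. Fewer trials also enter the verbal-time analysis.
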